### **7.4 Criteria for withdrawal / discontinuation of participants**

Participants are allowed to withdraw from the study at any time and for any reason. They do not have to share the reasons with the investigator. They will be asked to return the IMD. If the decision to withdraw is made by the investigator, the PI will inform the subject in person that they are no longer needed for the study. Reasons for withdrawing a participant from the study could be for non-compliance during testing, unreliable responses, medical reasons such as an ear infection, or the study may need to be stopped or postponed. Any data gathered from these subjects will be used for the current study. All data will remain encoded because results are only recorded using the identification code of the subject. There are normally at least five “back-up” test participants on the list to replace those that withdraw or are withdrawn. The “back-up” participants will have already been screened and deemed to be appropriate for the study.

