#### **9.3.3 Lab/Third visit**

Final Visit, Day 20 +/- 7: Otoscopy is performed. The subjects return the completed product questionnaires. They perform the lab test with the AMP in one condition: aided with P3. They complete a preference questionnaire during the appointment. They are notified that the trial has ended and those that normally wear hearing aids can return to using their own devices. They will return the IMD to the clinic. Any AEs are reported in the CRF. Those that are on the Bernafon subject list and normally wear devices fitted by the Bernafon clinic are reminded to return to the clinic for normal maintenance of their hearing aids. Anyone that would like to join the Bernafon clinic are also welcome to do so.

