- The effect of the instrument, i.e. the sound generation principle greatly varies between a string, a woodwind and a brass instrument. This might affect the perception of sound and interact with the range of the instrument, the hearing loss degree and type,
- The effect of amplification through hearing aids when musicians are playing. All the above-mentioned tests are based on passive listening experience. There are no publications, to the best of our knowledge, about the use of auditory feedback to control the production of music. We can assume that adaptation of their own voice production to the environment (Lombard effect) and perception of sound might show similarities when playing music,
- The effect of the IP which follows guidelines for hearing aids fitted to musicians. The guidelines are based on a project (Greasley et al., 2019) but no results based on quantitative research were published. It is therefore not possible to estimate an effect size when a personalized protocol like the IP is used with musicians.

The uncertainty from the test design and the unknown effect size from the IP motivates the choice for a larger sample size. Regarding recruitment possibilities, based on the principal investigator's input, the sample size was set to 18-20 participants for the current study.

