#### **11.4.2 Primary Analysis**

The study will assess the performance of the IP in comparison to the SP using a preference questionnaire. After wearing the devices for at least 10 +/- 7 days and using them in daily life and various music situations, the subjects will be asked to complete a preference questionnaire and choose between the two music programs (SP and IP).

The preference score is rated on a 5-points Likert scale: SP much better, SP better, no difference, IP better, IP much better. The score distribution is described by the minimum, median, and maximum values and tested with a Wilcoxon signed-rank test with the assumption that ordinal scores from a Likert scale reflect the within subject difference. The null hypothesis is that there is no difference between the tested protocols and the alternative hypothesis is that there is a preference for a protocol. A two-sided test will be made as the IP has not been tested before.

Certainty and motivation of preference will be summarized and described separately. The results of this test will be used to answer the 1st and 2nd research questions.

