3.2 Randomization

The study is based on repeated measures with the SP and the IP. Participants are asked to switch between the listening programs in a given condition (practice, rehearsal, or concert) in order for them to gather comparable experiences while playing and listening to music.

Program allocation effect, i.e. higher likelihood to use program 2 than 3, will be compensated by randomizing the order of the tested protocols in the listening program slot. This risk is outbalanced by the benefit of directly comparing the same listening situation with both programs.

The program order will be randomized, and the lab test order will follow the program order randomization. The active participation of the investigator is required for the IP resulting in a single blind (participant only) design. The randomization list will be provided to the investigator by the statistician and documented before the recruitment process starts.

The randomization list will be generated with a random permuted block method and a random digit link to control any potential order inequality. Pocock (1983, p 77) provides a link between random digits and the structure of blocks for four patients and 2 treatments (order). No stratification is foreseen because no confounding factors have been identified at this stage of the study design.

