4. STATISTICAL PRINCIPLES

4.1 Levels of confidence intervals and p-values

Inferential statistical tests will be performed using the two-sided $\alpha = 0.05$. All reported p-values greater than or equal to 0.001 will be rounded to three decimal places and p-values less than 0.001 will be displayed as " <0.001 ". Confidence intervals are computed from observed data at 95%.

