4.2 Analysis populations

The analysis of the primary outcome will be based on the intention-to-treat (ITT). The ITT population will include all participants with associated primary outcome data, excluding only subjects who were deemed ineligible following screening visit, those who withdrew from the trial, were unwilling for their previously collected data to be utilised or those who failed to provide baseline.

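### An unblinded investigator may withdraw and replace participants for undefined unreliable responses; withdrawal before the visit 3 preference leaves no primary outcome, and SAP 4.2 conflicts with the Protocol on withdrawn participants

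*Protocol*

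**What the plan says.** **Withdrawal and replacement.** Protocol 7.4 says of withdrawal by the investigator: "Reasons for withdrawing a participant from the study could be for non-compliance during testing, unreliable responses". It then adds medical reasons and the study being stopped or postponed. It gives no definition of unreliable, no threshold and no time limit, and does not ask for a decision made blind to program. A list of normally at least five screened back-ups supplies replacements. The same section then says that data gathered from withdrawn participants will be used. Protocol 8.3 says the same for those who ask to discontinue.

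**Blinding.** SAP 3.2 states: "The active participation of the investigator is required for the IP resulting in a single blind (participant only) design". Protocol 6.1.1 leaves the randomisation list open to the investigator, and Protocol 12.1.1 has the investigator enter the data.

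**Timing of the primary outcome.** It is collected once, at the final visit. Protocol 9.3.3 says: "They complete a preference questionnaire during the appointment". That step is listed after the return of questionnaires and the music perception (AMP) test with P3. Under Protocol 9.2.2 the music ratings for P2 and P3 also come back at this visit.

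**Analysis set.** Protocol 11.4.1 requires primary outcome data. Among those who withdrew, it excludes only people who also refuse the use of their data. SAP 4.2 has a comma where the Protocol joins the two conditions with an and, so "those who withdrew from the trial" reads as an exclusion in its own right. Protocol 11.5 and SAP 6.3 impute nothing and leave a participant with missing data out of that analysis. Protocol 10.1, on withdrawal for pain, names removal of partial data as one of its purposes.

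**The concern.** Removing a participant because of how they respond, when the person deciding knows which program is which, is a post-randomisation exclusion that may be related to the outcome. Before the preference exists, the investigator has heard the participant's comments while tuning the IP and has the visit 2 AMP result with P2. If the questionnaires are looked at on return, the P2 and P3 ratings are known too. Protocol 3.1 also records the expectation that the optimized program will do better.

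Bad faith is not needed. If honest judgements of unreliability fall more often on people who do not warm to the IP, the remaining sample leans towards it. With 18 to 20 participants and one preference score each, a few such removals matter. Five back-ups are 5/20 = 25% to 5/18 = 28% of the planned sample.

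**Working it through.** **1. The plan's own figure.** Protocol 11.2 says "the sample size was set to 18-20 participants for the current study", by precedent and recruitment, and also "It is therefore not possible to estimate an effect size when a personalized protocol like the IP is used with musicians". No effect size, SD or power is given, so 18-20 cannot be reproduced. For scale, the standardised paired effect detectable with 80% power at two-sided 0.05 is (1.960 + 0.842)/√n. That is 2.802/√18 = 0.66 and 2.802/√20 = 0.63.

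**2. When a participant leaves the primary analysis.**

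| Situation | Protocol 7.4, 8.3, 11.4.1 | SAP 4.2 as punctuated |
|---|---|---|
| Withdrawn after giving the preference, allows use of data | Kept | Excluded |
| Withdrawn before giving the preference | Data kept, but no primary outcome, so not analysed | Not analysed |
| Withdrew and refuses use of data | Excluded | Excluded |

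The first row is a conflict between the documents. The second is a gap even when every document is followed exactly: the retention rule cannot keep a preference that was never asked for.

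**3. Possible size.**

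*Inputs from the documents*
- n = 18 or 20 (Protocol 11.2).
- Wilcoxon signed-rank test on a 5-point preference score. Protocol 11.4.2: "A two-sided test will be made as the IP has not been tested before".
- SAP 4.1: "Inferential statistical tests will be performed using the two-sided" α of 0.05.

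*Assumed inputs, none of them in the documents*
- No true preference. The scores from SP much better to IP much better have probabilities 10/25/30/25/10% or 15/35/0/35/15%.
- The k participants least favourable to the IP are withdrawn and replaced by k random back-ups, with k = 0, 1, 2, 3 or 5.
- Participants are ranked for withdrawal on A = ρL + √(1 − ρ²)·e, where L is the underlying preference and e is independent noise. ρ = 1 is selection on the preference itself; ρ = 0.7 is selection on a correlated earlier rating.

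*Test.* Zeros dropped; normal approximation with tie and continuity corrections; 40,000 runs per case. The Monte Carlo standard error near 5% is √(0.05 × 0.95/40,000) = 0.0011, or 0.1 percentage point.

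*Two-sided rejection rate (range over both n and both distributions)*

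| k | Excluded and replaced, ρ = 0.7 | Excluded and replaced, ρ = 1 | All preferences kept, back-ups added |
|---|---|---|---|
| 0 | 4.2-4.7% | 4.2-4.7% | 4.2-4.7% |
| 1 | 5.6-6.2% | 6.9-7.5% | 4.2-4.9% |
| 2 | 7.7-8.2% | 11.3-12.8% | 4.2-4.8% |
| 3 | 9.9-10.7% | 16.9-18.4% | 4.3-4.9% |
| 5 | 14.4-15.5% | 27.8-30.8% | 4.3-4.8% |

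Most of the excess favours the IP. At k = 2, rejections in that direction are 6.8-7.4% (ρ = 0.7) and 10.6-12.1% (ρ = 1).

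**4. Matching columns to gaps.** Withdrawal before the questionnaire can only use earlier information, so ρ = 0.7 is the nearer case, and ρ could well be lower. ρ = 1 is an upper bound: it needs recorded preferences to be dropped, which only the literal SAP reading allows. The last column is Protocol 7.4 applied to recorded preferences, and also the result of the fix below.

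**The case against.** The strongest reply is that Protocol 7.4 itself retains data from withdrawn participants, supported by 8.3, and that 8.5 promises a summary from all recruited participants. This stands for any preference already recorded: if it is followed, the error rate does not rise. It does not help a participant who leaves before being asked.

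A reader might infer that SAP 4.2 settles the matter by dropping everyone who withdrew. The documents do not support that. The parallel sentence in Protocol 11.4.1 joins withdrawal to refusal, and SAP 1.2 shows version 1.0 written against protocol version 1.0, while the Protocol is now version 2.0. A lost conjunction is the likely explanation. It is still a conflict in the text that governs the primary analysis.

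A reader might also infer that the plan gives the investigator a direct way to choose the result after reading the program ratings. No text says that ratings are reviewed before the preference is given, or that anyone is withdrawn on that basis. Ratings and preference belong to the same appointment of at most two hours, and 9.3.3 lists the steps without fixing a strict order. The earlier signals are weak: tuning comments concern the IP only, before any field comparison, and the visit 2 AMP covers P2 only. What stands is that the sequence is permitted, not that it is prescribed.

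There are partial safeguards. Protocol 12.1.2 requires the reason for withdrawal on the CRF, and the number analysed is reported for each analysis. These make removals visible without limiting them. The exploratory label lowers the stakes, but a test at 0.05 is still planned and is to answer the first two research questions.

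**Conclusion.** The point holds as two specific gaps. First, an investigator who knows the allocation can withdraw someone for undefined unreliable responses before the preference is given, and that person then leaves the primary analysis under either document. Second, SAP 4.2 as punctuated contradicts Protocol 7.4, 8.3 and 11.4.1 on participants who have already given a preference, and Protocol 10.1 adds wording on data removal that fits neither 7.4 nor 8.3.

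The size is an illustration only. Two selective withdrawals, excluded and replaced, take the nominal 5% to about 8% under selection on a rating correlated 0.7 with preference, or to 11-13% under selection on preference itself. If preferences are kept there is no inflation. These figures rest on the assumed score distributions, correlation and number withdrawn. They do not say that selective withdrawal is planned or likely. The change is worth making because it costs little and closes both gaps.

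**What to change.** - **Protocol 7.4.** State that once both programs have been fitted at visit 2, response quality alone is not a ground for removal, and that the preference is still requested and counted in the primary analysis.
- **AMP data.** Flag unreliable AMP runs in the CRF by a criterion set in advance, before data are coded by program. Leave them out only in a sensitivity analysis.
- **Back-ups (Protocol 7.4 and SAP 4.2).** State that a back-up is an addition and does not remove the original participant from the analysis set.
- **SAP 4.2.** Match Protocol 11.4.1, so that withdrawal excludes only those who also refuse the use of their data.
- **Protocol 10.1.** Reconcile the data-removal wording with 7.4 and 8.3.
- **Report.** List each withdrawal with its timing, its reason and any preference given.

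Withdrawal for medical reasons or at the participant's own wish is not affected. The cost is a few sentences in the two documents, and some noisy responses that stay in the main analysis.

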## **8. STUDY INTERVENTION**

### **8.1 Identity of Investigational Products (medical device)**

The treatment will be approximately 20 days of use with the devices. For the first field test of 10 +/- 7 days they will use the devices to become accustomed to the amplification. For the second field test lasting 10 +/- 7 days they will use the devices with an additional two programs (IP and SP) to try when listening to music.

There will be three lab tests (one at each appointment) during which the participants will use the IMD, for up to 2 hours during testing in the clinic.

#### **8.1.1 Experimental Intervention (medical device)**

The investigational product (IMD) is a medical device. It is the current version of the marketed Bernafon hearing device. The name is Viron 9. It was released to the market in early 2019. One BTE hardware style will be used for the trial. It is called a BTE miniRITE (MNR) and is appropriate for mild to profound hearing losses (depending on the speaker that is used). The device uses a disposable battery that lasts for approximately 5-7 days of use.

The BTE MNR is fitted with the body of the device over the ear, and the speaker covered with a dome or earmold inside of the ear canal. The performance of the IP is expected to be the same or better than the SP. They are non-invasive devices. The dome that is worn inside the ear canal is made from non-toxic plastic and the earmolds are made of non-toxic plastic with an acrylic coating. An illustration of the IMD is shown in Figure 1.

Figure 1. Viron 9 miniRITE

#### **8.1.2 Control Intervention (comparator medical device)**

No Reference Medical Device (RMD) will be used for the trial as the comparison is between two programs which will both be fitted in the IMD.

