### **6.1.3 Other methods of minimising bias**

The IMD will be programmed with a P1 to be used in general listening situations. All test subjects will wear the hearing aids for the first field test of 10 +/- 7 days with this program to become accustomed to the amplification. They will continue to use P1 during the second field test with the SP and IP added as the second and third programs. P1 will serve as a control in the circumstance that the subject's rate both the music programs poorly, to determine whether only the music programs are the problem or whether they have not accepted the device overall.

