#### 9.2.3.1 Adverse events

For the recording of adverse events the subjects will be asked for a description of the event including time/date of onset, how long it lasted, how many times it occurred, and if it caused discomfort or pain or a disruption of hearing ability.

Before the end of each appointment, the subjects will be asked if they have experienced any adverse events. It will be explained that adverse events are not restricted to problems related to the hearing aids or their hearing but can include allergies, broken legs, headaches, etc. They will be recorded on the AE forms in the CRF.

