### **9.3 Procedures at each visit**

#### **9.3.1 Screening/First visit**

Screening visit, Day 0: The potential participants will be given the Patient Information and Informed Consent form. The trial will be explained including how many visits are expected as well as the type of testing that they will complete. They are given time during the appointment to read the information and decide whether to participate in the study. If they choose to not take part in the study, they will not sign the consent form, and the appointment will finish. If they choose to join the trial, they will sign and date the consent form. No trial activities will be performed before the consent form is signed and dated by the subject and the investigator. Subjects will receive a copy of the signed consent form. A hearing history is then taken, and otoscopy is performed. A hearing test is performed, and inclusion/exclusion criteria will be determined. The subject is then randomized regarding the assignment of the music programs (IP or SP) to program slots 2 or 3. They are fitted with the IMD based on a first fit in the software and adjusted using REM data to match the gain targets. The hearing aids will be fit only with a general program in the P1 slot. They will perform the lab test with the AMP in two conditions: unaided and aided with the general program. They are given an IFU for the hearing device. They are given a product questionnaire and a music perception questionnaire and instructed to complete them at home a day before their next appointment. Any AEs are reported in the CRF. They are scheduled for the second visit.

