#### **9.3.2 Fitting/Second visit**

Fitting Visit, Day 10 +/- 7: Otoscopy is performed, and the subjects return the completed questionnaires. The IMDs are fitted with IP and SP as specified by the randomization carried out at the first visit. The IP is optimized and fine-tuned based on comments that the subject makes about the sound while they play their instrument in the clinic. The SP is programmed without any adjustment based on the default music program offered in the software. They are instructed to switch between programs two and three when playing and listening to music for the next 10 +/- 7 days. They perform the lab test with the AMP in one condition: aided with P2. The subjects are given the music perception questionnaires and instructed to complete them at home a day before their next appointment. One questionnaire pertains to P2 and the other to P3. Any AEs are reported in the CRF. They are scheduled for the third visit.

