### 10.1.2 Definition and Assessment of (Serious) Adverse Events and safety related events

#### Adverse Event (AE)

Any untoward medical occurrence, unintended disease or injury or any untoward clinical signs (including an abnormal laboratory finding) in participants, users or other persons whether or not related to the investigational medical device [ISO 14155: 3.2].

This includes events related to the investigational device or the comparator and to the procedures involved. For users or other persons this is restricted to events related to the investigational medical device.

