6.4 Harms / Safety Data

The adverse event risks of taking part in the study have been assessed to be low in the study protocol. Numbers of adverse events and serious adverse events will be cross-tabulated for the IMD and categorised by severity. No formal statistical analysis will be conducted, but AEs and SAEs will be closely monitored throughout the process.

[figure not shown]
Serious Adverse Events (SAEs) will be recorded and the site will notify the trial monitor of any SAE, who will then notify the project sponsor within one working day.

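### The planned adverse event table pools P1-only time with IP/SP time, and program in use at onset is not among the event details listed

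*Protocol*

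**What the plan says.** **Comparison.** Protocol 8.1.2 uses no reference device because "the comparison is between two programs which will both be fitted in the IMD". Section 8.2.2 confirms that the control is the SP, programmed into the same hearing aid.

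**Adverse event analysis.** SAP 6.4 plans: "Numbers of adverse events and serious adverse events will be cross-tabulated for the IMD and categorised by severity". It then adds: "No formal statistical analysis will be conducted, but AEs and SAEs will be closely monitored throughout the process". Protocol 11.4.5 plans the same. Neither section mentions program or field period.

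**Sequence of programs.** At visit 1, "The hearing aids will be fit only with a general program in the P1 slot" (Protocol 9.3.1). IP and SP are loaded at the second visit, "Fitting Visit, Day 10 +/- 7" (9.3.2). P1 then stays in use: "They will continue to use P1 during the second field test with the SP and IP added as the second and third programs" (6.1.3).

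**What is recorded per event.** Protocol 9.2.3.1 asks for a description "including time/date of onset, how long it lasted, how many times it occurred", and whether there was discomfort, pain or disturbed hearing. Section 10.1 has participants questioned at every appointment and rates causality against the device or the study procedure.

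**Scope.** The adverse event definition in 10.1.2 states: "This includes events related to the investigational device or the comparator and to the procedures involved". The safety objective in 4.4 is the overall safety of the IMD, including any new risk factors since market release.

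**The concern.** The hearing aid has been on the market for almost a year. The new element is the IP, which Protocol 11.4.2 describes as not previously tested. If the trial met a new risk, the IP would be an obvious place to look, and the planned table cannot point there.

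The programs differ in a property tied to the expected complaints. Protocol 10.1.1 lists headache, excessive loudness and tinnitus as likely, and names a gain reduction among the responses to each. Section 3.6 says the SP gives 1 to 4 dB more gain than P1 at some frequencies. Sections 8.3 and 9.3.2 say the IP starts from P1 gain and is then tuned to the participant's comments.

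At stake is the wording of the report. It could state that the IP was preferred and give an adverse event total, while the reader could not see whether events arose before the IP was fitted or, afterwards, under which program.

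**Working it through.** The plan gives no adverse event rate, and its sample size comes from published ranges and recruitment potential. There is no figure of its own to reproduce.

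**1. Shape of the planned table.** One IMD and no reference device (Protocol 8.1.2, 8.2.2) give one column, with rows by severity.

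**2. How much time is pooled.** Inputs: visit 2 on day 10 ± 7, so days 3 to 17; visit 3 on day 20 ± 7, so days 13 to 27 (Protocol 9.1); second field period of 10 ± 7 days, so 3 to 17 days (Protocol 8.1).

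P1-only share = day of visit 2 / day of visit 3.

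- Nominal: 10/20 = 50%.
- Smallest: visit 2 on day 3, followed by the longest second period, 3 + 17 = day 20. Share 3/20 = 15%.
- Largest: visit 2 on day 17, followed by the shortest second period, 17 + 3 = day 20. Share 17/20 = 85%.

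The third constraint matters. Pairing day 3 with day 27 would give 3/27 = 11%, but implies a second period of 27 − 3 = 24 days, beyond the 17-day limit.

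**3. What the recorded data can recover.**

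- *Field period: yes.* Onset time or date (9.2.3.1), visit dates (12.1.1) and questioning at each appointment (10.1) place each event before or after the visit 2 fitting.
- *Program after visit 2: no, from the sources described.*
  - Program in use is not among the details in 9.2.3.1.
  - The causality rating in 10.1 does not separate programs, since P1, SP and IP are all the device.
  - Data logging gives average hours per program (8.4) and is not tied to an event.
  - The yes/no safety questions are in the product questionnaire, which is answered once, for P1, after the first field period (5.2, 9.2.3). Section 9.3.3 mentions product questionnaires coming back at visit 3, but 9.3.2 hands out only music questionnaires.
  - The music questionnaire covers artifacts for all three programs (SAP 6.1.4), but as a performance item; it is not an event record.

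**4. What 18 to 20 participants can show.** The true risks below are assumptions, because the documents give none. Chance of seeing at least one affected participant = 1 − (1 − p)^n:

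- p = 1%: 17% (n = 18) to 18% (n = 20).
- p = 5%: 60% to 64%.
- p = 10%: 85% to 88%.

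If no participant has a given event, the one-sided 95% upper limit is 1 − 0.05^(1/n): 15.3% for n = 18 and 13.9% for n = 20. A split by program can describe where events fell but cannot support a claim that one program produces more.

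**The case against.** The strongest defence is that the table answers the question asked. Protocol 4.4 and SAP 6.1.5 aim at overall IMD safety. The planned program contrasts concern preference and music perception, and no section plans a safety contrast of IP against SP. The wording in 10.1.2 about the comparator defines which events count and does not call for a comparator column. This stands: the plan is consistent with its own objective.

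A reader might infer that the trial cannot tell events before the music programs were loaded from events after. The documents do not support that. It is true of the planned table only, because onset and visit dates are collected.

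A reader might also infer that the IP raises gain and so is the likelier source of harm. The documents do not say so. Section 8.3 lets tuning move gain either way, and the SP itself adds gain over P1.

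Attribution by program would also be weak for some events. The first period is for acclimatisation, so a before/after split mixes getting used to amplification with change of program. Participants switch freely, so program at onset says little about lasting complaints such as headache or tinnitus. Raw counts would partly follow wearing time, since the music programs are meant for music situations. All of this stands, and it shapes the fix without removing the case for it.

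Finally, the adverse event form and the reporting SOP are not in the public documents, and a figure in SAP 6.4 is not shown. The form may already hold a program field. The text of 9.2.3.1 and the two analysis sections would still need to say so.

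**Conclusion.** The point holds as a gap in attribution and reporting. The planned table merges P1-only time (50% of device days on the nominal schedule, 15% to 85% for an individual) with time when IP and SP are also available. The period split needs no new data. The program split after visit 2 cannot be made from the details listed. The percentages assume that device days run from visit 1 to visit 3 and that all three windows in Protocol 8.1 and 9.1 are respected.

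This does not contradict the safety objective, and nothing in the documents indicates that the IP is less safe. The change is worth making because it is cheap and because program in use cannot be reliably reconstructed afterwards. With 18 to 20 participants the gain is descriptive.

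**What to change.** 1. In Protocol 11.4.5 and SAP 6.4, replace the single device column with two: onset before and onset after the visit 2 fitting. Show the number of participants with an event as well as the number of events. State how an event that recurs across visit 2 is counted.
2. Add one item to Protocol 9.2.3.1 and the adverse event form: program in use at onset (P1, P2, P3, not worn, unknown). Decode P2 and P3 to IP and SP from the randomisation list at analysis. The participant answers by program position, so blinding is unaffected.
3. Present the post-visit-2 counts beside the logged hours per program (Protocol 8.4), because the music programs are expected to be worn less than P1. The documents do not say when the log is read; a reading at visit 2 as well as visit 3 would separate P1 hours by period.
4. Label the table descriptive, and state that free switching and acclimatisation limit attribution of lasting events such as headache or tinnitus.

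**Cost.** The period split uses data already collected. The program split needs one form field, in place before the first participant is fitted. Some answers will be unknown.
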